The favorable outcomes of DS AML (EFS 80% or greater) have been achieved by different study groups with a variety of treatment approaches. Studies by COG and legacy groups, for example, have used 6 cycles in A2971 and AAML0431. A Japanese study group achieved similar results with only 5 cycles. Interim data for the ongoing DS AML study DS-ML 2006 by the BFM study group presented at the COG Fall Meeting in 2014 showed an OS of 90% with treatment using 4 cycles of chemotherapy ([name], pers. communication). Outcomes appear to be a function of treatment intensity (in the context of increased sensitivity of DS AML blasts to cytarabine, anthracyclines, and etoposide) rather than of the number of treatment cycles. The same conclusion appears to follow from the successful reduction of treatment cycles for non-DS AML from 5 in AAML0531 to 4 on AAML1031 in keeping with the approach of the MRC in the UK. Thus, on AAML1531, standard risk DS AML patients will receive 5 cycles of less intensive therapy and high risk DS AML patients will receive 4 cycles of more intensive therapy.

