## 2.9

### **Interim Analysis of Patients Treated on the Standard Risk Arm**

According to the study analysis plan, an interim analysis of treatment outcomes for lack of efficacy on the Standard Risk (SR) arm (Arm A) was performed after 50% of the expected number of EFS events had been observed (after 8 of 16 events). Based on a model generated using data of SR patients in the historical control (predecessor study AAML0431) and the amount of follow-up available at the time of data cut off (30 June 2018), 2.4 EFS events were expected in SR patients compared to 8 EFS events observed. The projected 2-year EFS for SR patients on AAML1531 is significantly lower than on AAML0431 (85.6% compared to 93.5%, p 0.0002). As of October 5, 2018, 9 of 109 SR patients on AAML1531 have experienced a relapse at 136 to 327 days after study entry. Four of these relapses occurred on therapy (1 during Intensification I, 3 during Intensification II) and 5 during the first 6 months of follow up after completion of protocol therapy. Of the 9 relapsed SR patients, 8 have died.

These data show lack of sufficient efficacy of AAML1531 protocol therapy for SR patients. Based on this information, post-Induction I treatment on the SR Arm A of AAML1531 was permanently closed.

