##### 2.10.2.2 Evaluation of Early Response of DS AML to Treatment by MRD

Data collected from 146 patients in the recently completed study AAML0431 provide direct evidence for the prognostic value of MRD measured by flow cytometry after Induction I in DS AML. The unique immunophenotype of DS AML blasts permitted their detection by multi-parameter flow cytometry at a level as low as 0.01% ([name], personal communication). EFS among 125 patients who were MRD-negative (MRD  $< 0.05\%$ ) was significantly higher than in 21 patients (14%) who were MRD-positive (93% v. 76% at 2 years; log-rank  $P = .007$ ). This difference extended to OS (2-yr OS 96% v. 76%, log-rank  $P < 0.001$ ), indicating that the prognostically unfavorable group of DS AML patients can be identified by MRD and that this cohort may benefit from intensification of therapy. Complying with the FDA requirement that the MRD cut-off be above the threshold of sensitivity of the assay, AAML1531 will use a cutoff of 0.05%. Based on the data of AAML0431, this cut-off safely captures the large majority of MRD-negative patients for the proposed reduction in therapy (only 5 patients had MRD levels between 0.01 and 0.1%, with 2 of these patients relapsing, 1 electively

withdrawing at the end of induction, and 2 patients remaining in remission).

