#### 4.1.3 Risk Group Assignment

After recovery from the Induction I, patients are assigned to either the Standard or High Risk Group based on the level of MRD in the bone marrow aspirate (approximately Day 28). If there is no sign of count recovery a bone marrow aspirate should be performed no later than Day 49 from the start of Induction I to rule out the presence of refractory MDS/AML.

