**Analysis Plan.** To determine feasibility, the proportion of cases will be recorded for which the design of a sufficiently sensitive primer and probe combination for digital PCR was successful by Day 28. Similarly, the proportion of cases will be determined for which the requirements for DNA quality and multiplex amplification were met. Library preparation, sequencing and bioinformatic analysis will follow previously established protocols. Positive and negative percent agreement of MRD results obtained on Day 28 will be compared between flow cytometry, digital PCR and ECS for each pair of detection methods. Corresponding 95% confidence intervals will be calculated for the percent positive and negative agreement for each pair of detection methods. McNemar's test will be used to compare percent positive and negative agreement for two detection methods relative to the third detection method. MRD results obtained with each method will be correlated with the probability of disease-free survival and the cumulative incidence of relapse.

**Relevance.** This direct comparison of methods is expected to determine the optimal method to measure treatment response by MRD and predict relapse risk in DS AML in the context of risk-based treatment assignment by flow cytometry based MRD. Results, therefore, will establish the foundation of accurate risk-based stratification of treatment intensity for future therapeutic trials in DS AML.

15.1.3 To establish a DS AML cell bank of viably frozen bone marrow samples and corresponding non-tumor DNA samples collected at end of induction.

**Background.** The exploratory aim 1.2.2 is to establish a biobank of viably frozen bone marrow samples from DS AML patients collected at the end of Induction I for future research.

**Experimental Plan.** Bone marrow cells will be collected at end of Induction 1 and viably cryopreserved for those patients who consent to this optional study. Bone marrow samples collected at the time point of MRD analysis, which in the majority of cases will be obtained at the time of morphological remission, will provide non-tumor DNA for genomic analyses of DS AML blasts.

**Relevance.** The repository of viably cryopreserved bone marrow samples of DS AML, remission samples and other sources non-tumor DNA will provide essential support for the objectives of this study and serve as a vital resource for future mechanistic studies in DS AML.

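### Section 15.1.2 relates each MRD method to relapse without allowing for the fact that flow MRD alone chose the treatment, so flow is likely to be understated against PCR and sequencing

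*Combined protocol and SAP*

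**What the plan says.** All references are to the combined protocol and SAP.

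- **Planned analysis.** Section 15.1.2, Analysis Plan: "MRD results obtained with each method will be correlated with the probability of disease-free survival and the cumulative incidence of relapse". No stratification by arm, adjustment or restriction is given.
- **Use of the result.** The Relevance paragraph of 15.1.2 expects the comparison to "determine the optimal method to measure treatment response by MRD and predict relapse risk in DS AML", and adds: "Results, therefore, will establish the foundation of accurate risk-based stratification of treatment intensity for future therapeutic trials in DS AML".
- **Treatment assignment.** Section 4.1.3: "patients are assigned to either the Standard or High Risk Group based on the level of MRD in the bone marrow aspirate". Sections 3.3.4 and 3.3.5 put the cut-off at 0.05%.
- **What each group received.** Before Amendment 4A, flow-negative children went to Arm A, without high-dose cytarabine (sections 2.2 and 15.1.1.1). For flow-positive children, section 2.7 says that "high risk DS AML patients will receive 4 cycles of more intensive therapy".
- **PCR and sequencing.** The opening of section 15.0 describes the exploratory studies as research only. Apart from the Induction I MRD result, findings are batched and not returned to the treating physician.
- **Outcome by flow group under treatment not guided by MRD.** Section 2.8 says that AAML0431 collected MRD blinded. Section 2.10.2.2 gives EFS of "93% v. 76% at 2 years" for MRD-negative and MRD-positive children.
- **Outcome on Arm A.** Section 2.9 gives the projected 2-year EFS, in percent, against AAML0431 as "85.6% compared to 93.5".

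**The concern.** Flow dichotomised at 0.05% and treatment arm are the same variable in this trial; the DNA results are not tied to the arm in that way. A correlation of flow with relapse therefore estimates prognosis combined with an arm contrast. On the documents' figures that contrast works against flow: flow-negative children received a therapy later closed for insufficient EFS, and flow-positive children received one intended to improve EFS. Children who were DNA-positive but flow-negative all received the reduced therapy.

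The three methods are thus compared with outcome on unequal terms. A flow assay with real prognostic value could look weak partly because the treatment it triggered worked. Since the plan wants the result to underpin later risk stratification, a misleading ranking could be carried into future trials.

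This is separate from the loss of standard-risk outcomes after Amendment 4A (sections 4.1.4 and 9.3.1). It remains in children enrolled earlier who have follow-up.

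**Working it through.** **1. The plan's own interim figure.** Section 2.9 reports 8 EFS events against 2.4 expected, p 0.0002. The one-sample log-rank statistic is Z = (8 − 2.4)/√2.4 = 3.61, one-sided p = 0.00015, which agrees on rounding. The documents' evidence that flow-negative children did worse on Arm A than on AAML0431 therefore reproduces.

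**2. Flow contrast under different treatments.** Inputs are 2-year EFS:
- flow-negative, AAML0431: 93% (2.10.2.2) or 93.5% (9.2)
- flow-positive, AAML0431: 76% (both sections)
- Arm A: 85.6%, projected (2.9)
- Arm B: 76% if intensification does nothing, 88% at the design alternative (9.2)

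Formula: HR = ln(S positive)/ln(S negative). It assumes proportional hazards and uses EFS as a proxy, because 15.1.2 plans DFS and relapse incidence but the documents give no two-group figures for them.

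| Scenario | S positive / S negative | HR |
|---|---|---|
| AAML0431 | 0.76 / 0.93 | 0.2744/0.0726 = 3.78 |
| AAML0431 | 0.76 / 0.935 | 0.2744/0.0672 = 4.08 |
| Arm A projected, Arm B no effect | 0.76 / 0.856 | 0.2744/0.1555 = 1.77 |
| Arm A projected, Arm B at target | 0.88 / 0.856 | 0.1278/0.1555 = 0.82 |

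To keep 4.08 with Arm A at 85.6%, Arm B EFS would have to fall to 0.856^4.08 = 0.53.

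**3. Uncertainty in the Arm A figure.** The exact Poisson 95% interval for 8 events is 3.45 to 15.76; divided by 2.4 this is a ratio of 1.44 to 6.57. (The projected 85.6% corresponds to ln 0.856/ln 0.935 = 2.31, inside that range.) At the lower limit Arm A EFS is 0.935^1.44 = 0.908, and the ratios are 0.2744/0.0967 = 2.84 (Arm B no effect) and 0.1278/0.0967 = 1.32 (Arm B at target). Flow is attenuated but not reversed. At the upper limit attenuation is greater: 0.935^6.57 = 0.643, giving 0.62 and 0.29.

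**4. Flow against a DNA test of equal true value.** The documents give no concordance between methods, so it is assumed. Let 15% be positive on each test, with the same HR of 4.08 under common treatment. Take P(DNA+ given flow+) from 30% to 90% and 2-year risk in discordant children from 10% to 20%. Then apply treatment by flow result only: hazard multiplier ln 0.856/ln 0.935 = 2.31 for flow-negative, and 1 or ln 0.88/ln 0.76 = 0.466 for flow-positive.

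Worked case (50%, 15%):
- Under common treatment, risk is (0.24 − 0.5 × 0.15)/0.5 = 0.33 in double-positives and 0.057 in double-negatives.
- On Arm A, risk becomes 1 − 0.85^2.31 = 0.313 if DNA-positive and 0.126 if DNA-negative.
- With no Arm B effect, flow is 0.240 v 0.143, HR 1.78; DNA is 0.322 v 0.129, HR 2.82.
- With Arm B at target, flow HR is 0.84 and DNA HR 2.13.

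| Whole range | Flow HR | DNA HR |
|---|---|---|
| Arm B no effect | 1.77–1.82 | 1.89–3.94 |
| Arm B at target | 0.82–0.90 | 0.97–3.75 |

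Flow looks worse than the equally good DNA test in every case tried. The DNA ratio also falls below 4.08, and the gap narrows as concordance rises.

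**5. Within arm.** In this model the DNA hazard ratio within each arm equals its common-treatment value. That follows from applying one hazard multiplier per arm; if the treatment effect differs by DNA status, the within-arm ratio describes prognosis under that arm's therapy. Flow at 0.05% is constant within each arm, so it has no within-arm contrast.

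**6. Events available.** Arm A: 9 relapses among 109 children (2.9). Arm B at n = 41: 41 × 0.24 = 9.8 or 41 × 0.12 = 4.9 EFS events.

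**The case against.** The strongest points on the other side, and what stands:

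- **The plan acknowledges the setting.** Relevance speaks of using MRD to "predict relapse risk in DS AML in the context of risk-based treatment assignment by flow cytometry based MRD". This stands as an acknowledgement, but no analysis step follows from it.
- **The scope is narrow.** Aim 1.2.1 concerns feasibility and analytical characteristics, no test comparing the methods on outcome is specified, and the plan is silent on pooling rather than calling for it. This stands. Percent agreement and McNemar's test do not use outcome and are unaffected. Relevance nevertheless claims an optimal method for predicting relapse risk.
- **The assay changed.** Section 2.10.2.2 says that AAML0431 relied on the leukaemia-associated immunophenotype and that this trial uses a different-from-normal method expected to be more accurate. A reader might infer that one marker falls from 3.8 to 0.8 through treatment assignment alone. The documents do not support that, nor the use of AAML0431's value as this assay's own.
- **The endpoint is a proxy.** EFS also counts deaths, second malignancies and remission failure (9.1). Relapse counts in 2.10.2.2 point to a larger contrast: 7/21 = 33% v 5/125 = 4%, if the denominators match. This stands as a limit on the size.
- **Hazards are not proportional in the SAP's own models.** The cure models in 9.3.2 give cumulative-hazard ratios of 5.7 at 1 year, 4.5 at 2 years and 2.9 at plateau. This also stands; the ratios are illustrations at 2 years.
- **The inputs are not results.** The 85.6% is a projection from 8 events against a historical control, and 88% is a design target. A reader might infer that the analysis is certain to misjudge flow or reverse it. That does not follow.

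**Conclusion.** The concern holds as a likely bias whose size is not known. Carried out without regard to arm, the outcome correlation in 15.1.2 confounds flow MRD with treatment by design. It is likely to understate flow relative to PCR and sequencing, whose associations are also distorted but usually less.

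On the documents' figures, a hazard ratio of 3.8 to 4.1 at AAML0431 values becomes about 1.8 or 0.8 with Arm A at its projection, and about 2.8 or 1.3 with Arm A near 91%. The first of each pair takes Arm B at 76%, the second at 88%. Reversal needs both an Arm A result close to its projection or worse and a successful Arm B, or an Arm A result near the upper limit of the interim excess.

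These figures rest on EFS as a proxy, proportional hazards, a historical comparison and, for flow against DNA, assumed concordance. They illustrate the mechanism and do not predict the trial's estimates. The aim is exploratory, but the use claimed for it makes the correction worthwhile.

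**What to change.** In section 15.1.2:

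1. Analyse DFS and cumulative incidence of relapse within flow-assigned arm.
   - Arm A children treated before Amendment 4A: by PCR status and by sequencing status, censored when taken off therapy at arm closure, as 9.3.1 already does for EFS.
   - Arm B children: by PCR, by sequencing and by quantitative flow level.
2. State that flow will not be ranked against the DNA methods on relapse across arms.
3. State that the prognostic value of flow dichotomised at 0.05% cannot be estimated in this trial. AAML0431 may be cited as context only, noting its different flow method.
4. Reword Relevance to: *added prognostic value of DNA-based MRD within flow-defined treatment groups*.

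The agreement analyses stay as they are. The cost is a few sentences and no new data. The price is low precision (9 relapses among 109 Arm A children, roughly 5 to 10 Arm B events at n = 41, and fewer of both because the GATA1 samples are optional) and no overall ranking of the three methods on outcome.

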**APPENDIX I: CTEP AND CTSU REGISTRATION PROCEDURES****INVESTIGATOR AND RESEARCH ASSOCIATE REGISTRATION WITH CTEP**

Food and Drug Administration (FDA) regulations and National Cancer Institute (NCI) policy require all individuals contributing to NCI-sponsored trials to register and to renew their registration annually. To register, all individuals must obtain a Cancer Therapy Evaluation Program (CTEP) Identity and Access Management (IAM) account at <https://ctepcore.nci.nih.gov/iam>. In addition, persons with a registration type of Investigator (IVR), Non-Physician Investigator (NPIVR), or Associate Plus (AP) must complete their annual registration using CTEP's web-based Registration and Credential Repository (RCR) at <https://ctepcore.nci.nih.gov/rrc>.

RCR utilizes five person registration types.

- IVR — MD, DO, or international equivalent;
- NPIVR — advanced practice providers (e.g., NP or PA) or graduate level researchers (e.g., PhD);
- AP — clinical site staff (e.g., RN or CRA) with data entry access to CTSU applications such as the Roster Update Management System (RUMS), OPEN, Rave, acting as a primary site contact, or with consenting privileges;
- Associate (A) — other clinical site staff involved in the conduct of NCI-sponsored trials; and
- Associate Basic (AB) — individuals (e.g., pharmaceutical company employees) with limited access to NCI-supported systems.

RCR requires the following registration documents:

Documentation Required	IVR	NPIVR	AP	A	AB
FDA Form 1572	✓	✓			
Financial Disclosure Form	✓	✓	✓		
NCI Biosketch (education, training, employment, license, and certification)	✓	✓	✓		
GCP training	✓	✓	✓		
Agent Shipment Form (if applicable)	✓				
CV (optional)	✓	✓	✓		

An active CTEP-IAM user account and appropriate RCR registration is required to access all CTEP and Cancer Trials Support Unit (CTSU) websites and applications. In addition, IVRs and NPIVRs must list all clinical practice sites and Institutional Review Boards (IRBs) covering their practice sites on the FDA Form 1572 in RCR to allow the following:

- Addition to a site roster
- Assign the treating, credit, consenting, or drug shipment (IVR only) tasks in OPEN
- Act as the site-protocol Principal Investigator (PI) on the IRB approval
- Assign the Clinical Investigator (CI) role on the Delegation of Tasks Log (DTL).

In addition, all investigators acting as the Site-Protocol PI (investigator listed on the IRB approval), consenting/treating/drug shipment investigator in OPEN, or as the CI on the DTL must be rostered at the enrolling site with a participating organization.

Additional information is located on the CTEP website at <https://ctep.cancer.gov/investigatorResources/default.htm>. For questions, please contact the RCR **Help Desk** by email at [[contact]](mailto:[contact]).

### **CTSU REGISTRATION PROCEDURES**

This study is supported by the NCI Cancer Trials Support Unit (CTSU).

#### **Requirements For AAML1531 Site Registration:**

- IRB approval (For sites not participating via the NCI CIRB; local IRB documentation, an IRB-signed CTSU IRB Certification Form, Protocol of Human Subjects Assurance Identification/IRB Certification/Declaration of Exemption Form, or combination is accepted )

#### **Submitting Regulatory Documents:**

Submit required forms and documents to the CTSU Regulatory Office using the Regulatory Submission Portal on the CTSU website.

To access the Regulatory Submission Portal log in to the CTSU members' website, go to the Regulatory section and select Regulatory Submission.

Institutions with patients waiting that are unable to use the Regulatory Submission Portal should alert the CTSU Regulatory Office immediately at [name] in order to receive further instruction and support.

#### **Checking Your Site's Registration Status**

Site registration status may be verified on the CTSU members' website.

- Click on *Regulatory* at the top of the screen;
- Click on *Site Registration*; and
- Enter the site's 5-character CTEP Institution Code and click on Go.
  - Additional filters are available to sort by Protocol, Registration Status, Protocol Status, and/or IRB Type.

Note: The status shown only reflects institutional compliance with site registration requirements as outlined within the protocol. It does not reflect compliance with protocol requirements for individuals participating on the protocol or the enrolling investigator's status with NCI or their affiliated networks.

### **Data Submission / Data Reporting**

Medidata Rave is a clinical data management system being used for data collection for this trial/study. Access to the trial in Rave is controlled through the CTEP-IAM system and role assignments.

Requirements to access Rave via iMedidata:

- A valid CTEP-IAM account; and
- Assigned a Rave role on the LPO or PO roster at the enrolling site of: Rave CRA, Rave Read Only, Rave CRA (LabAdmin), Rave SLA, or Rave Investigator.

Rave role requirements:

- Rave CRA or Rave CRA (Lab Admin) role must have a minimum of an Associate Plus (AP) registration type;
- Rave Investigator role must be registered as an Non-Physician Investigator (NPIVR) or Investigator (IVR); and
- Rave Read Only role must have at a minimum an Associates (A) registration type.

Refer to <https://ctep.cancer.gov/investigatorResources/default.htm> for registration types and documentation required.

### **Data Quality Portal**

The Data Quality Portal (DQP) provides a central location for site staff to manage unanswered queries and form delinquencies, monitor data quality and timeliness, generate reports, and review metrics.

The DQP is located on the CTSU members' website under Data Management. The Rave Home section displays a table providing summary counts of Total Delinquencies and Total Queries. DQP Queries, DQP Delinquent Forms and the DQP Reports modules are available to access details and reports of unanswered queries, delinquent forms, and timeliness reports. Review the DQP modules on a regular basis to manage specified queries and delinquent forms.

The DQP is accessible by site staff that are rostered to a site and have access to the CTSU website. Staff that have Rave study access can access the Rave study data using a direct link on the DQP.

To learn more about DQP use and access, click on the Help icon displayed on the Rave Home, DQP Queries, and DQP Delinquent Forms modules.

Note: Some Rave protocols may not have delinquent form details or reports specified on the DQP. A protocol must have the Calendar functionality implemented in Rave by the Lead Protocol Organization for delinquent form details and reports to be available on the DQP. Site staff should contact the LPO Data Manager for their protocol regarding questions about Rave Calendaring functionality.

**APPENDIX II: WHO CLASSIFICATION OF AML****Acute myeloid leukemia and related neoplasms**

Acute myeloid leukemia with recurrent genetic abnormalities

AML with t(8;21)(q22;q22); *RUNX1-RUNX1T1*

AML with inv(16)(p13.1q22) or t(16;16)(p13.1;q22); *CBFB-MYH11*

APL with t(15;17)(q22;q12); *PML-RARA*

AML with t(9;11)(p22;q23); *MLLT3-MLL*

AML with t(6;9)(p23;q34); *DEK-NUP214*

AML with inv(3)(q21q26.2) or t(3;3)(q21;q26.2); *RPNI-EVII*

AML (megakaryoblastic) with t(1;22)(p13;q13); *RBM15-MKL1*

*Provisional entity: AML with mutated NPM1*

*Provisional entity: AML with mutated CEBPA*

Acute myeloid leukemia with myelodysplasia-related changes

Therapy-related myeloid neoplasms

Acute myeloid leukemia, not otherwise specified

    AML with minimal differentiation

    AML without maturation

    AML with maturation

    Acute myelomonocytic leukemia

    Acute monoblastic/monocytic leukemia

    Acute erythroid leukemia

        Pure erythroid leukemia

        Erythroleukemia, erythroid/myeloid

    Acute megakaryoblastic leukemia

    Acute basophilic leukemia

    Acute panmyelosis with myelofibrosis

Myeloid sarcoma

Myeloid proliferations related to Down syndrome

    Transient abnormal myelopoiesis

    Myeloid leukemia associated with Down syndrome

Blastic plasmacytoid dendritic cell neoplasm

